## Study Objectives and Specific Aims

In this study, we will assess the clinical efficacy and safety of CoQ10 (ubiquinol) in 200 veterans with GWI, in a classic double-blind, randomized, placebo-controlled trial, with 100 participants per treatment arm of the study. Subjects will be recruited at four geographically different sites.

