
The clinical and laboratory testing is performed without knowledge of the subjects' group membership, the group A vs B true condition will remain blinded throughout the study until its conclusion. There are two treatment conditions: CoQ10 (ubiquinol) 400mg for 2 months followed

by 200mg maintenance for 4 months and placebo taken once a day in the morning with food. The subject schedule includes 5 on-site assessments. On-site assessments include the screening visit with informed consent, the drug initiation visit, an 8 week visit and the 16 and 24-week visits. In addition, there is a web based self-report assessment given every 4 weeks throughout the treatment period and at 4 weeks after completion of the study drug. A member of the research team may contact the participant by phone to remind him or her to complete the surveys on the computer. Subjects will also utilize an activity monitor (FitBit) device to assess activity and sleep throughout the study period through 7 months. **(Assessments, see Table 1.)** 

The CSR&D Data Monitoring Committee (DMC) and the local VA pharmacist will have the authority to break the blind and recommend stopping the study should one group have evidence of adverse effects or significant efficacy in group A or B that would ethically require the blind to be broken. Further details regarding the interim efficacy analysis and formal efficacy stopping rules are provided in the statistical section below. There will be no formal stopping rules for safety; the DMC may recommend stopping the study for any concerns they feel jeopardize the safety of patients in the trial regardless of resulting p-values. The research pharmacist will also have access to an electronic emergency unblinding system developed by the CSP Pharmacy Center should an individual subject event require the blind be broken to access appropriate care (e.g., a toxic reaction to a product requiring treatment). This decision would follow institutional guidelines, following a discussion with the treating clinician. All subjects will have a physical examination, medical history, and will be given a battery of psychometric questionnaires.

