## Data Analysis Plan

## Statistical considerations

**General Statistical Approach:** Patients will be randomized in a 1:1 manner to Coq10 or placebo; randomization will be stratified by study center and gender. This study includes a comprehensive survey of patient status using a broad set of clinical assessments and laboratory assays designed to assess the response to treatment Unless otherwise specified, two-sided P < 0.05 will be considered statistically significant. Statistical analyses will be carried out using SAS Version 9.4 or higher.

**a) Baseline:** Differences in continuous baseline variables will be compared by a two-sample t test. The Mann-Whitney U test will be used in the case of non-normal distribution. For baseline categorical variables, Fisher's exact test will be used.

**b)** Evaluating the efficacy of CoQ10 in GWI: The primary analysis is to compare treatment groups on change from baseline SF-36 physical function score over time (6 monthly time points from Week 4 to Week 24) in a repeated measures setting using a final two-sided 0.049 level of significance (a 0.049 level is being used at the end of the study instead of 0.05 to account for the interim analysis further described below). This will be carried out using a mixed model (MM) analysis of variance (ANOVA) with effects for treatment, time, baseline physical function score and the randomization strata of study center and gender. The within-patient correlation structure will be assumed to be unstructured. If this analysis shows a significant treatment difference across time or a significant treatment-by-time interaction, comparisons across treatment (significance level at each time point using a Bonferroni alpha-adjustment (significance level at each time point = 0.049 divided by 6, the number of planned post-baseline time points) to account for the multiple comparisons. Data will be analyzed as an intention-to-treat model; i.e., all

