randomized subjects will be included using available data (i.e., a patient does not have to provide data through the end of the study to be included in the analysis; this is the strength of the MM ANOVA approach). A secondary supportive analyses will be carried out where missing physical function data at each time point are first imputed via monotone multiple linear regression imputation, under the assumption the missing data mechanism is missing at random prior to carrying out the mixed model analysis. The imputation regression model at each time point will include randomized treatment, measures of the primary outcome at earlier time points and baseline covariates that will be specified in the final detailed statistical plan. Fifty imputed datasets will be created, and the MM ANOVA will be run on each data set; the 50 MM ANOVA results will then be combined across the data sets using PROC MIANALYZE in SAS to obtain one overall assessment of treatment difference on the imputed data.

**c) Sample size justification and power analysis:** In this study population, we rely on the literature of Phase III studies of other inflammatory states to determine assumptions required for sample size calculations. Our primary clinical outcome variable is physical function of the SF36 measured over time (approximately monthly from week 4 through week 24; i.e., 6 measurements over time). Our current data suggests a coefficient of variation (CV) of approximately 0.40 for physical function at a given time point. Assuming this and assuming a relative increase in SF36 of at least 21% for Coq10 over placebo at each time point, then there is a 0.525 treatment effect size at each time point. Under this effect size, power is at least 95% to detect a treatment difference over time using an evaluable group sample size of n=90 subjects at a two-sided 0.049 level of significance regardless of the within- patient correlation between time points. To account for approximately 10% attrition, 100 subjects per group will be randomized. Such an evaluable sample size will also allow at least 80% power to detect a relative increase t of 21% separately at each time point after using a Bonferroni multiple comparison adjustment across the six time points.

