**f) Safety Endpoints:** The primary safety variable is the incidence of treatment emergent adverse events (TEAEs). A TEAE is an event that emerges, or a pre-existing event that worsens, any time after initiation of first study treatment. Adverse events will be coded by using the most recent released version of MedDRA at the time of study start. The incidence of TEAEs will be presented overall and by MedDRA system organ class and preferred term. TEAEs will also be presented by

severity (mild, moderate, or severe). Patients experiencing more than one occurrence of the same preferred term or system organ class will be categorized under the maximum severity experienced for that preferred term or system organ class. Similar analyses of TEAEs will be conducted by relationship to drug. Patients experiencing more than one occurrence of the same preferred term or system organ class. This will be repeated for serious TEAEs. Descriptive statistics (sample size, mean and median, quartiles, minimum and maximum) of laboratory values will be presented for each visit in which they were collected. Similarly, descriptive statistics from the change from baseline to each visit will be presented. Box plots of the changes from baseline will be presented across visits.

g) Evaluation of blinding: Each subject and investigator will be asked at the end of their follow-up to guess whether they believe the subject was randomized to active treatment or sham group. Frequencies of correct and incorrect responses will be provided separately for subjects and for investigators.

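### The blinding check scores guesses only as correct or incorrect by type of guesser; without a split by assigned arm it cannot tell random guessing from a shared belief in active drug, or say which arm recognised its treatment.

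*Combined protocol and SAP*

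**What the plan says.** The evaluation of the blind is described in one place, item g) of Statistical considerations in the Data Analysis Plan. On timing: "Each subject and investigator will be asked at the end of their follow-up". The question is to "guess whether they believe the subject was randomized to active treatment or sham group". The summary is: "Frequencies of correct and incorrect responses will be provided separately for subjects and for investigators". Nothing else in the document adds a table of guess by assigned arm, a blinding index, a 'don't know' answer or a criterion for reading the result.

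The context comes from elsewhere in the document:

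- **Allocation:** "Patients will be randomized in a 1:1 manner to Coq10 or placebo".
- **Size:** "To account for approximately 10% attrition, 100 subjects per group will be randomized".
- **Primary analysis:** to "compare treatment groups on change from baseline SF-36 physical function score over time". Table 1 lists the SF-36 among the self-report variables.
- **Maintenance of the blind:** under Entry Criteria, "the group A vs B true condition will remain blinded throughout the study until its conclusion".

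**The concern.** A single percent correct mixes two quantities: how often CoQ10 subjects say active, and how often placebo subjects say placebo. Different states of the blind can give the same figure, so the table may not tell a reader what happened.

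This matters because the primary endpoint is the subject's own rating. If the trial is positive, readers will ask whether subjects on CoQ10 knew what they were taking. The Safety section hopes for better energy on treatment and allows that sleep may suffer as a result. The background attributes the weaker result of the higher split dose in the earlier crossover trial to a stimulating bedtime dose. These are possible cues to assignment. A check meant to address that question should show the pattern in each arm.

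**Working it through.** The plan gives no figure for the blinding check, so there is nothing of its own to reproduce. The check is direct arithmetic.

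**Inputs from the plan.** Allocation is 1:1. With 100 randomised per arm and about 10% attrition, 100 × (1 − 0.10) = 90 subjects per arm remain.

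**Assumptions.** The guess patterns are illustrative. Every guess is taken as active or placebo, with equal numbers of guesses in the two arms.

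**Formulas.** Let *a* be the share guessing active in the CoQ10 arm and *p* the share guessing active in the placebo arm.

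- Pooled share correct = [a + (1 − p)] / 2 = 0.5 + (a − p)/2.
- Bang index in an arm = share correct − share incorrect. This is 2a − 1 for CoQ10 and 1 − 2p for placebo.

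**Results.**

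| Pattern | a | p | Pooled correct | Index, CoQ10 | Index, placebo |
|---|---|---|---|---|---|
| Random guessing | 0.50 | 0.50 | (0.50 + 0.50)/2 = 50% | 0 | 0 |
| Most guess active in both arms | 0.80 | 0.80 | (0.80 + 0.20)/2 = 50% | +0.6 | −0.6 |
| All guess active | 1.00 | 1.00 | (1.00 + 0)/2 = 50% | +1 | −1 |
| Only CoQ10 arm above chance | 0.90 | 0.50 | (0.90 + 0.50)/2 = 70% | +0.8 | 0 |
| Both arms above chance | 0.70 | 0.30 | (0.70 + 0.70)/2 = 70% | +0.4 | +0.4 |

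The planned table shows the first three patterns as identical and the last two as identical. The indices by arm separate all five.

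**Precision for subjects.** The variance of the index in one arm is 4q(1 − q)/n, where q is the share correct, and it is largest at q = 0.5. With n = 90 the 95% half-width is at most 1.96 × 2 × √(0.25/90) = 0.207, so about 0.21. This assumes independent guesses, one per subject. It does not carry over to investigators, who would each guess for many subjects at four sites.

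**The case against.** The strongest reply is that the pooled figure already measures what matters most. Because it equals 0.5 + (a − p)/2, it is a rescaling of the difference in belief between arms, and that difference is what can bias a comparison of arms. The two 70% patterns share the same difference, 0.40, so giving them one value is not wrong. When 80% of both arms say active, a figure of 50% correctly reports no differential recognition. This stands, and it limits the point to interpretation: the planned table detects a difference but does not describe or locate it.

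It also rules out two stronger readings. A reader might infer that unblinding confined to one arm would go unseen, but the 90%/50% pattern moves the figure to 70%. Only its attribution to an arm is lost. A reader might also treat a shared belief in active drug as unblinding. Such guesses carry no information about allocation, so the pattern is response bias.

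A third reading is that the protocol expects subjects to notice the active drug. It does not go that far. The gain in energy is a hope and the effect on sleep a possibility. Morning dosing is meant to avoid sleeplessness. Gastrointestinal effects, although named as the commonest complaint, are put below 1% in the studies cited, and the matching placebo has the same other ingredients.

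The plan also does not forbid a table by arm, and its silence on a 'don't know' answer does not show that the form lacks one. A correct guess cannot be scored without the assigned arm, so the table could be produced later. That is true, but the plan names the split it intends and arm is not in it. Stating the arm split now removes any appearance of choosing it after the result.

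Finally, a guess made at the end of follow-up may reflect felt improvement. That limits any index taken then, including the one proposed, and should be stated.

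**Conclusion.** The point holds as a weakness in a descriptive summary. As written, item g) cannot separate random guessing from a shared belief in active drug (both 50%), and cannot attribute an above-chance result to one arm or both (70% in either case). It would still show that some differential recognition had occurred.

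The size rests on 1:1 allocation, equal numbers of guesses per arm and assumed guess patterns. The documents give no ground for predicting which pattern will occur or for saying that the blind will fail. The primary test is unaffected, and no decision rule depends on this table. The change is worth making because the endpoint is self-reported and the better table uses data the plan already needs.

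**What to change.** In item g), replace the sentence on frequencies with:

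> Guesses are cross-tabulated by assigned arm, separately for subjects and investigators, and the Bang blinding index is given for each arm, with a 95% CI for subjects.

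Add two statements. Investigator guesses are clustered, so they are reported descriptively or with a cluster-adjusted interval. Guesses at the end of follow-up may reflect perceived benefit as well as unblinding.

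A 'don't know' answer is optional. If the form does not have one, adding it is a small change to the form, and the downside is fewer definite guesses. The same edit can change sham to placebo in the question.

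The cost is one table. Apart from the optional answer, no new data are needed, and sample size, alpha and the primary analysis stay as they are.

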## Data and Safety Monitoring Plan

#### **Risk management and Emergency Response:**

This study has been assigned for administrative and scientific oversight to the Clinical Services Research and Development Data Monitoring Committee (DMC) to [name] and his staff based at the Hines VAMC. They will monitor the study for safety, efficacy, and progress. Study participants will be asked to self-monitor and report to study personnel any episodes of symptoms. Adverse reactions will be reported to the Project Manager ([name]) who will communicate with [name], the local IRB, and the DMC. While other trials have not seen serious adverse reactions, standard protocols are in place, with moderate to severe reactions r e p or t ed to both the IRB and the DMC All unanticipated problems involving risk to subjects or others, serious adverse events, and all subject deaths associated with the protocol will be reported. Comments will be recorded on the outcomes of the event or problem. In the case of a serious adverse event, an assessment will be made on the relationship to the participation in the study. All reports determined by the investigators or DMC to be possibly or definitely related to study participation and reports of events resulting in serious adverse events will be promptly forwarded to the VACO ORD.

Should a systemic allergic reaction occur, subjects are advised to call 911, and take an antihistamine while awaiting response. The most common complaint with ubiquinol is GI upset and diarrhea. This is handled by taking the medication with food and if necessary with dose adjustment to 50%. All of the VA medical centers have a VA Emergency room that is available 24/7 if for some reason the study physician or back up is not available.

Veterans are the study population and are cared for by the VA health care system, which will assume the costs of study related injuries. Women of childbearing years are asked to take measures to avoid pregnancy during the study. Barrier methods or better are sufficient.

## **Psychological Safety Plan**

We aim to ensure the safety of psychological study participants. Specific objectives of this safety plan are to ensure that:

- 1. Participants requesting assistance receive prompt response from mental health professionals who are knowledgeable safety risk assessment
- 2. The study team responds when participant's affect or behavior raises concerns (e.g., expressions of extreme distress), even if the participant him or herself does not request help.

The study team will check the on-line questionnaire HAM-D Question #3 regarding suicidality and will alert [name]. [name] will call the participant by telephone to assess the situation. If necessary, she will transfer the participant to the national VA Suicide Prevention Hotline. She will give the veteran the toll free number for the national VA Suicide Prevention [contact]-[name]) so that veterans, regardless of proximity to the Miami VA Healthcare System, can receive assistance in case of emergency. The hotline directs veterans to a VA professional who can immediately address their crisis situation. The local Suicide Prevention Coordinator then provides follow-up and assurance that these veterans in crisis receive on-going care. The study team will record and report to the IRB any incidents they are made aware of in which a participant calls the suicide prevention hotline. During the on-site assessment, if the Research Coordinator or Principal Investigator assesses a risk to the participant, she will walk with the participant to the Miami VA ER.

Because the study is based at the Miami VA, the study team will take additional measures to inform the Miami VA mental health after-hours and ER staff about this study. Specifically, we will distribute an information letter describing the study and listing the contact information for the study PI and Research Coordinator.

#### **Risk Assessment Personnel**

Professionals assessing potential risk in participants include Research Coordinator, Principal Investigator, VA Suicide Prevention Hotline staff, Miami VA ER and after-hours mental health staff. The Research Coordinator and Principal Investigator will assess risk in participants during administration of the structured clinical interview, completion of questionnaires or when participants request that a member of the study team contact them during regular business hours because of distress. The Principal Investigator will assess risk in participants in situations where the Research Coordinator identifies a potential need for intervention. The VA Suicide Prevention Hotline will conduct assessments among veterans who call the hotline. The Miami VA ER and After-Hours Mental Health Staff will conduct assessment and management of distressed veterans who call after hours. The Research Coordinator will be responsible for managing communication among these professionals to provide continuity of care as needed and report any adverse events among participants to the IRB.

## Safety

Coenzyme Q10, (ubiquinol) is widely used as an overly the counter supplement and is considered to be safe by the FDA, with rare reports of side effects. We will be monitoring for symptoms that suggest allergic reactions (rash, stomach upset) or any other medication related side effect. It is hoped that the medications will improve your energy levels. Should this happen, there is a possibility that it will interfere with sleep. If this occurs, we will assess the benefit of reducing the dose. Dosing schedules will be reviewed at the investigators meeting before study initiation, and standard operating procedures to handle any perceived drug intolerance such as GI side effects will be addressed by the clinicians. Typically, a dose modification, reducing the dose by half for a week then increasing back to the target range over 2 weeks can be employed to determine if the presumptive associated side effect recurs. In the final analysis, we will review blood levels to determine if drug levels predict response or adverse reaction.

Adverse reactions of drug intolerance will be categorized by severity, body system, and number of events per individual studied. Serious reactions will be reported promptly to the IRB and CSR&D Data Monitoring Committee (DMC). Study personnel, including the PI, who also is the Director of the GWI clinic, will be available by telephone 24/7 and in clinic during routine hours. The Miami VAMC Emergency Department will serve as back up should a serious adverse reaction occur when personnel are not available.

## **Risks/ Benefits Assessments for Ubiquinol**

Both ubiquinone and ubiquinol have been used extensively in clinical trials and in clinical settings. Whether efficacious or not, one remarkable observation is the reassuring safety profile of both preparations. Ubiquinone has been used in dosages up to 4,500 mg per day in frail populations (Parkinson's) and has seen positive results at the dosages proposed in this study in congestive heart failure and in illnesses known to be secondary to mitochondrial disorders (reviewed in Kern 2011, Kizhahkkedath 2013).

The most common adverse effects are gastrointestinal in nature and can include nausea, epigastric pain, diarrhea, heartburn, and appetite suppression. However, the prevalence of these adverse effects was less than 1% in reported studies (Jelin, 1999). Gastrointestinal effects of CoQ10 may be lessened with a dosage reduction or may subside with continued therapy. Asymptomatic elevations in s er um lactate dehydrogenase and hepatic enzymes were observed and may occur with oral dosages of CoQ10 in excess of 300 mg/day; however, cases of serious hepatotoxicity have not been reported (Greenberg, 1990; Micromedix, 2014). If female veterans are pregnant, are breastfeeding, or become pregnant, ubiquinol might involve risks to the embryo or fetus, which are currently unforeseeable. For this reason, you will be required to take a pregnancy test in the beginning of the study and use adequate protection to prevent pregnancy. There is the possibility that ubiquinol may interfere with sleep and may lower blood pressure. For participants who commonly have very low blood pressure, they should check blood pressure carefully. For the virtual platform, if the clinician learns that the potential participant has a history of low blood pressure, then the participant will be excluded from the virtual study option. In congestive heart failure studies, clinical relapse was noted on withdrawal of CoQ10, whereas reinstatement of therapy resulted in improvement (Mortenson, 1990; Mortenson, 1985). We selected a formulation that has been used in prior clinical trials in other disease states and have safety data, bioavailability data as well as efficacy data published (Chandran et al., 2012; Sanmukhani et al., 2014; Kizhakkedath et al., 2013; Kern, 2011). Based on the literature review of treatment responses in other illnesses and [name] experience, and conversations with Kaneka Nutrients (the primary source of ubiquinol in the USA) we will use ubiquinol 200 mg (the equivalent of ubiguinone 600mg) after a 2 month "loading" of 400 mg to correct deficiency states. It will be given as a morning dose, with food, to avoid evening side effects of sleeplessness and to optimize its bioavailability.

